9.3.1.5. Multiple-gestation pregnancies

Multiple-gestation pregnancies will be enrolled in the registry. Each fetus/infant will be assigned a unique identifier and included in the main analysis population (Section 9.7.1); however, for the analyses of preterm birth, SGA, and postnatal growth deficiency, multiple-gestation pregnancies will be excluded from the main analysis population due to the higher risk of these outcomes in twins and higher-order multiples.

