9.7.3.3. Calculation of outcome prevalence

Prevalence rates of the outcomes of interest will be calculated according to the conventions described in Table 4. In general, the prevalence of each outcome will be calculated by dividing the number of cases of the outcome by the appropriate denominator for that particular outcome, based on clinical knowledge and/or the methodology used by the external comparator. Prevalence is preferred over incidence when examining pregnancy outcomes, such as congenital malformations, because incidence cannot be reliably estimated given the complexities in the reproductive process.⁶⁷

For most outcomes, the main analysis population (denominator) will be the number of pregnant women with pregnancy outcome data, the number of live births, or the number of infants with follow-up data at the timepoint of interest, as appropriate; however, for some outcomes, the main analysis population (denominator) will be restricted based on certain relevant factors:

- For MCM, prevalence in the rimegepant-exposed cohort will be calculated among the subset of women who are exposed during the first trimester.
- For MCM, prevalence will be calculated among live births for the primary analysis, and a secondary analysis will be conducted among live births and fetal losses.
- For preterm birth, SGA, and postnatal growth deficiency, prevalence will be calculated among singleton live births due to the higher risk of these outcomes in twins and higher-order multiples.
- For live birth and infant outcomes (ie, preterm birth, SGA, postnatal growth deficiency, and infant developmental delay), prevalence will be calculated among live births/infants without MCMs.
- For postnatal growth deficiency, infants born preterm or SGA will be excluded from the main analysis population (denominator).
- For infant developmental delay, infants born preterm will be excluded from the main analysis population (denominator).
- For SAB and preterm birth, prevalence will be calculated among the subset of women who are enrolled in the registry prior to 20 and 37 gestational weeks, respectively.
- For some outcomes, prevalence will be calculated at multiple timepoints. For example, postnatal growth deficiency and infant developmental delay will be assessed at 2, 4, 6, and 12 months of

PFIZER CONFIDENTIAL

infant age. At each timepoint, prevalence will be calculated among infants with data available for the particular outcome at that timepoint.

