For comparison with external comparators, the prevalence rates of the outcomes of interest among the rimegepant-exposed participants of the main analysis population will be calculated according to the conventions used by the selected external comparators. For example, for the comparison with MACDP, live births and stillbirths with MCMs (including MCMs not associated with medication exposure) will be included in the numerator, and the denominator will be the number of live births. The MACDP calculates rates by this convention, which increases sensitivity. Likewise, for comparisons with the external cohort of pregnant women without migraine (from the retrospective pregnancy outcomes study), the conventions used to calculate outcome prevalence rates in the internal and external cohort will be aligned.

In addition, "crude" prevalence rates, without limitations and exclusions, may be conducted to avoid restricting the main analysis population (denominator). For example, infants with MCM and/or infants born preterm may be included for the prevalence rate calculation of infant developmental delay.

Outcome	Numerator	Denominator	
Primary Outcome – MCM			
Primary analysis: among live births with 1 st trimester exposure (if applicable for cohort)	Live births with confirmed MCMs (excluding MCMs not associated with medication exposure) among women with pregnancy outcome data and exposure during 1 st trimester (if applicable)	Live births among women with pregnancy outcome data and, if applicable, exposure during 1 st trimester	
Secondary analysis: among all pregnancy outcomes with 1 st trimester exposure (if applicable for cohort)	Live births and fetal losses with confirmed MCMs (excluding MCMs not associated with medication exposure) among women with pregnancy outcome data and, if applicable, exposure during 1 st trimester	Live births and fetal losses among women with pregnancy outcome data and, if applicable, exposure during 1 st trimester	
Secondary analysis: among live births with exposure at any time during pregnancy (if applicable for cohort)	Live births with confirmed MCMs (excluding MCMs not associated with medication exposure) among women with pregnancy outcome data and, if applicable, exposure at any time during pregnancy	Live births among women with pregnancy outcome data and, if applicable, exposure at any time during pregnancy	

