Comparison with external comparator (EUROCAT) ⁴⁴	TOPFA among women with pregnancy outcome data	Live births and stillbirths among women with pregnancy outcome data
Preterm birth		
Primary analysis between internal cohorts	Singleton preterm live births without MCMs among women with pregnancy outcome data who are enrolled (and exposed, if applicable) prior to 37 gestational weeks	Singleton live births without MCMs among women with pregnancy outcome data who are enrolled (and exposed, if applicable) prior to 37 gestational weeks
Comparison with external comparator (Pfizer Study C4951006)	Preterm live births among women with pregnancy outcome data who are	Live births among women with pregnancy outcome data who are

PFIZER CONFIDENTIAL

Outcome	Numerator	Denominator
	enrolled (and exposed, if applicable) prior to 37 gestational weeks	enrolled (and exposed, if applicable) prior to 37 gestational weeks
SGA		
Primary analysis between internal cohorts	Singleton live births without MCMs who are SGA based on weight/length/head circumference among women with pregnancy outcome data	Singleton live births without MCMs with weight/length/head circumference data among women with pregnancy outcome data
Comparison with external comparator (Pfizer Study C4951006)	Live births who are SGA based on weight among women with pregnancy outcome data	Live births among women with pregnancy outcome data
Postnatal growth deficiency		
Primary analysis between internal cohorts (at 2, 4, 6, and 12 months)	Singleton infants without MCMs who were not born preterm or SGA with postnatal growth deficiency based on weight/length/head circumference among infants with weight/length/head circumference data at the time point	Singleton infants without MCMs who were not born preterm or SGA with weight/length/head circumference data at the time point
Infant developmental delay	-	
Primary analysis between internal cohorts (at 2, 4, 6, and 12 months)	Infants without MCMs who were not born preterm with developmental delay in a particular category among infants with developmental milestone data for the category at the time point	Infants without MCMs who were not born preterm with developmental milestone data for the category at the time point

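### The Table 4 comparisons of preterm birth and SGA with Study C4951006 count all live births without adjustment, so unequal twin shares, or unequal missing birth weights for SGA, could shift the ratio without any drug effect

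*Protocol*

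**What the plan says.** Section 9.3.1.5 enrols multiple gestations, but "for the analyses of preterm birth, SGA, and postnatal growth deficiency, multiple-gestation pregnancies will be excluded from the main analysis population". The reason given is "due to the higher risk of these outcomes in twins and higher-order multiples". Section 9.7.3.3 repeats the rule: "For preterm birth, SGA, and postnatal growth deficiency, prevalence will be calculated among singleton live births". Neither place states an exception.

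The internal rows of Table 4 follow the rule; the preterm numerator is "Singleton preterm live births without MCMs among women with pregnancy outcome data who are enrolled" before the gestational-age cut-off. The rows for Study C4951006 (the sponsor's parallel retrospective study, used for women without migraine) do not. The preterm numerator is "Preterm live births among women with pregnancy outcome data who are" enrolled before 37 weeks, and the SGA numerator is "Live births who are SGA based on weight among women with pregnancy outcome data". Both denominators are live births, with no limit to singletons.

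Section 9.7.3.3 explains the difference. For external comparisons, registry rates "will be calculated according to the conventions used by the selected external comparators", and for the retrospective study "the conventions used to calculate outcome prevalence rates in the internal and external cohort will be aligned". Section 9.7.3.2 compares registry and external rates by exact methods, with confidence intervals and p-values, and mentions no covariate adjustment. Weighting is described in sections 9.7.3.1 and 9.7.3.4 for the cohorts within the registry.

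**The concern.** The protocol recognises that multiples distort preterm birth and SGA. It removes them from the internal comparison, where weighting is also available, but leaves them in the external comparison, where no adjustment is described. A common counting rule gives a fair comparison only if the share of twins is similar in both studies. One is a volunteer registry and the other a retrospective study, so similarity cannot be taken for granted. Each twin pregnancy also adds two infants to the counts.

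The SGA row raises a second question. The internal row's denominator requires measurements; the C4951006 row's denominator is all live births. An infant with no recorded weight, or born outside the 24 0/7 to 42 6/7 week range of the growth standard in section 9.3.4.8, cannot be classed as SGA but still counts in the denominator. This lowers the observed rate, which in a safety study is the direction that hides a signal.

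**Working it through.** **The plan's own figures.** Table 3 gives power above 99.0% for a 2.5-fold increase with 390 per cohort at two-sided 0.05. The pooled normal approximation gives 99.90% for preterm birth (8.47% reference) and 99.99% for SGA (10.0%), so both reproduce. Neither is in dispute. The documents give no twin frequency or twin risk, so what follows rests on assumptions.

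**Twin share and preterm birth.** Inputs:
- Singleton preterm risk 8.47%. This is the Table 3 reference rate, used here as a singleton rate by assumption; Table 3 describes it as a general-population rate.
- Twin preterm risk t = 60%, with 50% as an alternative (assumed).
- Twin share of pregnancies m = 3% in C4951006 and 1.5% to 6% in the registry (assumed).
- No drug effect and no migraine effect.

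Rate per live-born infant = [(1 − m) × 0.0847 + 2m × t] / (1 + m).

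For C4951006 at t = 60%: (0.97 × 0.0847 + 0.06 × 0.60) / 1.03 = 0.1182 / 1.03 = 11.47%. Twins then supply 0.036 / 0.1182 = 30% of preterm births.

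| Registry twin pregnancies | Rate, t = 60% | Ratio, t = 60% | Ratio, t = 50% |
|---|---|---|---|
| 1.5% | 9.99% | 0.87 | 0.89 |
| 3% | 11.47% | 1.00 | 1.00 |
| 4% | 12.43% | 1.08 | 1.07 |
| 5% | 13.38% | 1.17 | 1.14 |
| 6% | 14.30% | 1.25 | 1.21 |

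If the shares are instead read as percentages of live births (p = 0.0847 × (1 − s) + t × s), 6% against 3% at t = 60% gives 11.56% / 10.02% = 1.15. The same 3% of pregnancies is 0.06 / 1.03 = 5.8% of infants, which accounts for the gap.

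**Chance of a nominal p < 0.05 with no drug effect.** This uses an exact binomial test with 316 infants (the evaluable number in Table 2), the external rate taken as fixed and infants as independent. For twin-pregnancy shares against 3%:
- equal shares: 4% to 5%
- 4% share: 8% to 9%
- 5% share: 15% to 19%
- 6% share: 26% to 35%

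Each range runs over t = 50% and 60%. Correlation within twin pairs and sampling error in the external rate are ignored.

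**With singletons only on both sides**, a difference in twin share contributes nothing.

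**SGA denominator.** If a fraction f of live births cannot be classified and this is unrelated to SGA status, the observed rate is (1 − f) times the true rate. The ratio between studies is (1 − f registry) / (1 − f C4951006). With f = 5% to 10% in the registry and none in C4951006 (assumed), the ratio is 0.95 to 0.90. With equal f it is 1.00.

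**The case against.** The strongest reply is that there is no contradiction to repair. Section 9.7.3.3 says denominators may follow the external comparator's method and that the two studies will be aligned. The C4951006 rows drop the exclusion of infants with malformations as well as the singleton limit, so they look like a chosen all-live-births convention. Restricting the registry side alone would create the mismatch that alignment avoids, and section 9.3.1.5 cannot bind another study. This stands.

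A reader might infer that the protocol compares singletons in the registry with all births outside it, or that a twin imbalance will show up as a rimegepant effect. The documents support neither. Both sides count live births alike, and nothing shows that twin shares differ. The comparison also sets exposed women with migraine against women without migraine. Section 7.3 reports that migraine itself is associated with preterm birth, so the comparison cannot isolate a drug effect whatever the plurality rule. Its p-values are nominal under section 9.7, section 9.9 uses these external data for context, and the internal preterm and SGA analyses are limited to singletons.

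The size is also open to challenge. A ratio of 1.25 needs twice the external twin share; 4% against 3% gives about 1.08. With 316 infants at 11.47%, the 95% interval on the ratio is about 0.74 to 1.36 even with the external rate fixed, so every ratio in the table lies within sampling error.

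On SGA, section 9.7.4 expects little missing critical data, birth weight is collected at pregnancy outcome (section 9.4.1.2), and equal missingness cancels. Against that, section 9.4.4 lets the woman report the outcome when the healthcare provider cannot be reached, so some missing weights are plausible, though no figure is given.

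Alignment still does not equalise the plurality mix or the missingness, and no adjustment is described for this comparison.

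**Conclusion.** The concern holds in a limited form. The all-live-births rows are a deliberate, aligned convention, but they leave a secondary comparison open to a source of bias that the protocol itself recognises and removes elsewhere. If twin shares differ, the crude preterm ratio could move in either direction, between about 0.87 and 1.25 under the stated assumptions. SGA is open to the same mechanism. Its row also lets unclassifiable infants dilute the rate in proportion to their number, cancelling only if that proportion is equal in both studies. Twin shares, twin risks, the singleton rate and the missing fractions are all assumed. The primary outcome and the internal preterm and SGA comparisons are unaffected.

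**What to change.** 1. Where C4951006 can identify plurality, make its Table 4 rows for preterm birth and SGA singleton-only in both studies. Keep the all-live-births figure as a descriptive addition.
2. Where it cannot, keep the aligned all-live-births rows, label them descriptive, and state the exception in section 9.3.1.5 with a reference to section 9.7.3.3 and Table 4.
3. Limit the SGA denominator to live births with birth weight, sex and a gestational age within the range of the growth standard, on both sides where the C4951006 data allow.

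The registry already collects number of fetuses and infant sex (section 9.3.5) and birth weight and gestational age at outcome (section 9.4.1.2). The cost is wording in two table rows, one extra tabulation from the parallel study, and the loss of the few multiple births from the main version of these comparisons. Whether C4951006 can supply that tabulation cannot be judged from this protocol.

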9.3.2. Disease of interest

A diagnosis of migraine (with or without aura) is a condition for inclusion into the internal study cohorts. For this study, the definition of migraine will be consistent with the International Classification of Headache Disorders, Third Edition.⁴ Disease information, including date of diagnosis and disease severity, will be collected from HCPs and/or participants.

9.3.3. Exposure of interest

Exposure to rimegepant is a condition for inclusion into the cohort of pregnant women with migraine who were exposed to rimegepant. In addition, pregnant women who were not exposed to rimegepant but who are exposed to other products for the treatment or prevention of migraine may be eligible for inclusion in the cohort of pregnant women who were unexposed to rimegepant. Finally, participants who were exposed to other CGRP antagonists (eg, ubrogepant), CGRP monoclonal antibodies, or ditans (eg, lasmiditan) will not be eligible for enrollment into either cohort. ANNEX 3 provides a list of products for the treatment or prevention of migraine. This list of medications will be continually updated to reflect relevant, newly approved medications.

Exposure will be defined as bodily uptake of any dose of rimegepant or other migraine product at any time during pregnancy (from conception to pregnancy outcome) or prior to pregnancy (up to 5 product half-lives prior to conception). Due to the short elimination half-life of rimegepant (11 hours), the prepregnancy exposure period for rimegepant is relatively short; participants will be considered exposed during pregnancy if a dose is taken up to 3 days prior to the date of conception.

Information on prescribed dose, route, frequency, start/end dates, and indication/reason for use (for migraine products—acute only, preventive only, or both) will be collected from HCPs at enrollment, at the end of the second trimester, and at the occurrence of the pregnancy outcome. For acute and preventive migraine therapies (prescription and non-prescription), exposure during pregnancy will additionally be captured in real time or near real time from the participants via an exposure diary/migraine log. See Section 9.4.1 for more information.

Exposure will be further categorized by trimester of exposure; Section 9.4.3 provides information on the methods used to determine gestational age and trimester of exposure.

PFIZER CONFIDENTIAL

9.3.4. Outcomes

9.3.4.1. Congenital malformations

The study will define and code congenital malformations using the criteria specified by the CDC MACDP and EUROCAT.^{40,41} A malformation may be described and classified by severity (eg, major malformation), by origin (eg, genetic, environmental exposure), and by organ system (eg, urogenital system or malformations known as congenital heart defects [CHD]). An MCM will be defined as any major structural or chromosomal defect detected in live-born infants, stillbirths/fetal losses ≥ 20 gestational weeks, and elective terminations of any gestational age.⁴⁰ This definition is consistent with, but not restricted to, the CDC MACDP and EUROCAT definitions.

To avoid misattribution of the malformation to the medication, MCMs not associated with medication exposure, such as chromosomal abnormalities, genetic syndromes, prematurity-related conditions in infants born at < 36 gestational weeks (eg, patent ductus arteriosus, patent foramen ovale, inguinal hernias, or undescended testes), and positional effects (eg, hip dislocation due to breech position or abnormal skull shape due to crowding by multiple fetuses), will not be considered MCMs in the statistical analyses comparing MCM prevalence between the internal cohorts.⁴² Given that the registry will also use the CDC's MACDP and EUROCAT as external comparators, the registry will include cases of MCMs not associated with medication exposure in the prevalence calculations for this comparison.

Transient malformations in term infants, whether occurring alone or with other malformations, will be reported in the study, as certain transient malformations may be associated with maternal medication exposure in pregnancy and can vary by age of detection and/or age of resolution (eg, CHDs).⁴³ Lastly, the MACDP only includes minor malformations if they occur in the presence of an MCM. However, as stated in the objectives, major and minor malformations are of interest for this study and both will be reported.

Live-born infants with only positional defects (malformations), infectious conditions, or with biochemical abnormalities will be classified and reported separately. The CDC MACDP has different objectives and reporting needs than this project, so a thoughtful adaptation of their guidelines is appropriate.

The registry will systematically collect information on major and minor structural malformations, transient malformations in term infants, and chromosomal defects that are apparent at birth and noted through infant age 1 year, including: congenital malformation(s) and details, if noted, type of congenital malformation(s) if applicable, attribution to drug therapy, and other factors that might have contributed to the outcome.

If a congenital malformation is reported, other data of interest can be collected through targeted followup.

PFIZER CONFIDENTIAL

9.3.4.2. Pregnancy outcome

Each **pregnancy outcome** will be reported as one of the following:

- Recognized SAB: fetal death or expulsion of products of conception occurring at <20 gestational weeks. Terminology may include missed abortion, incomplete abortion, and inevitable abortion.
- Elective termination: voluntary interruption of pregnancy, including pregnancy termination that occurs electively, to preserve maternal health, or due to abnormalities. Participants who have an elective termination will be further categorized based on presence of fetal anomalies:
- TOPFA: voluntary interruption of pregnancy after prenatal diagnosis⁴⁴ of fetal anomaly
- Stillbirth: a fetal death occurring at ≥20 gestational weeks, or if gestational age is unknown, a fetus weighing ≥350 g
- Live birth: an infant born alive (any Apgar score >0)

9.3.4.3. Pre-eclampsia

Pre-eclampsia will be defined as high blood pressure and signs of liver or kidney damage (eg, proteinuria) occurring at >20 gestational weeks.^{45,46}

9.3.4.4. Eclampsia

Eclampsia will be defined as seizures or coma in a pregnant woman with pre-eclampsia.⁴⁵

9.3.4.5. Gestational hypertension

Gestational hypertension will be defined as high blood pressure occurring at >20 gestational weeks without signs of liver or kidney damage (eg, proteinuria).⁴⁶

